9.7.1.1.1 Demographics

Demographic data to be collected include: age, date of birth, gender, race, ethnicity, height, weight and BMI.

Height in metres (to the nearest cm) and weight in kilograms (to the nearest 0.1 kilogram) in indoor clothing and without shoes will be measured. Body Mass Index = Body weight (kg) / [Height (m)]² will be calculated.

9.7.1.1.2 Medical History and Concurrent Conditions

Relevant medical history and current conditions will be recorded in the CRF.

9.7.1.1.3 Physical Examination

A Physician will perform a physical examination. The examination will include: Ear/nose/throat, ophthalmological, dermatological, cardiovascular, respiratory, gastrointestinal, central nervous system, lymph nodes and musculoskeletal systems. Other body systems can be examined if required, at the discretion of the Investigator.

9.7.1.1.4 Virology

Virology screen will include: Hep B, Hep C and HIV.

Virology will be analysed by the local laboratory according to their local procedures.

9.7.1.1.5 Drugs of Abuse and Alcohol

Urine alcohol and drugs of abuse screen will include: Cannabinoids, amphetamines, benzodiazepines, opiates and cotinine.

Drugs of abuse and alcohol samples will be analysed by the local laboratory according to their local procedures.

9.7.1.1.6 Pregnancy Test, Menstrual and Obstetric History

Part 2 only: Pregnancy tests will be performed on all female subjects regardless of postmenopausal or sterilised status. Pregnancy tests will be performed by the local laboratory according to their local procedures.

9.7.1.2 Compliance with Inclusion/Exclusion Criteria

The Investigator will assess all participants against the study inclusion and exclusion criteria at the Screening Visit. Compliance will be re-confirmed at Baseline.

9.7.1.3 Efficacy Assessments

Not applicable to this study

GB-HV-01 Clinical Study Protocol Confidential RD 676/25641 Version: FINAL 6.0 / 05 April 2016 Page 52 of 73

9.7.1.4 Safety Assessments

Safety assessments will be performed during the study at the time-points specified in the Study Flow Charts and include:

9.7.1.4.1 Adverse Events

AEs and serious adverse events (SAEs) that occurred during the study along with their severity and relationship to study drug will be reported.

An AE is defined as:

Any untoward medical occurrence in a patient or clinical study subject administered a medicinal product and which does not necessarily have a causal relationship with this treatment.

An unexpected adverse reaction is defined as:

An adverse reaction, the nature, or severity of which is not consistent with the applicable product information (e.g. investigator's brochure for an unapproved investigational product or summary of product characteristics (SmPC) for an authorized product)

AEs will be monitored throughout the study from the first dose through to the follow-up post study visit. All AEs should be recorded, whether considered minor or serious, drug-related or not.

All abnormal laboratory findings considered to be clinically significant must be recorded as AEs.

Recording of Adverse Events

All of the following details should be recorded in the subject's CRF for each AE:

- Full description of AE.
- Date and time of onset.
- Date and time of resolution.
- Severity of event, to be assessed by the investigating physician in accordance with the definitions below.
- Relationship to IMP to be assessed by the investigating physician in accordance with the definitions below.
- Action taken (if any).
- Outcome and details of any further follow-up.

Grades of Adverse Event Severity

The following grades should be used by the investigating physician to describe the severity of AEs.

The following are the only grades which should be used to describe AE severity. Only 1 severity grade should be used for each AE (e.g. mild - moderate is not acceptable).

GB-HV-01 Clinical Study Protocol Confidential RD 676/25641 Version: FINAL 6.0 / 05 April 2016 Page 53 of 73

SEVERITY OF THE AE	DEFINITION
Mild AE	The AE does not interfere with the subject's daily routines. It causes no more than slight discomfort
Moderate AE	The AE interferes with some aspects of the subject's daily routines.
Severe AE	The AE causes inability to carry out the subject's daily routine.

Definitions of Adverse Event Causality

The following definitions should be used by the investigating physician to describe the relationship between an AE and the IMP.

The following are the only definitions, which should be used to describe the relationship between AEs and the IMP. Only 1 relationship definition should be used for each AE (e.g. possible-probable is not acceptable).

RELATIONSHIP TO IMP	DEFINITION
Almost Definite	 Distinct temporal relationship with drug treatment. Known reaction to agent or chemical group, or predicted by known pharmacology. Event cannot be explained by subject's clinical state or other factors.
Probable	 Reasonable temporal relationship with drug treatment. Likely to be known reaction to agent or chemical group, or predicted by known pharmacology. Event cannot easily be explained by subject's clinical state or other factors.
Possible	 Reasonable temporal relationship with drug treatment. Event could be explained by subject's clinical state or other factors.
Unlikely	 Poor temporal relationship with drug treatment and/or Event easily explained by subject's clinical state or other factors.
Unrelated	 Event occurred before dosing or Event or intercurrent illness due wholly to factors other than drug treatment.

Serious Adverse Events

"SAE", "serious adverse reaction" or "unexpected serious adverse reaction" is defined in Statutory Instrument 2004 No. 1031 as any AE, adverse reaction or unexpected adverse reaction, respectively, that

- a. results in death,
- b. is life-threatening,
- c. requires hospitalisation or prolongation of existing inpatients' hospitalisation,
- d. results in persistent or significant disability or incapacity, or

GB-HV-01 Clinical Study Protocol Confidential RD 676/25641 Version: FINAL 6.0 / 05 April 2016 Page 54 of 73

e. consists of a congenital anomaly or birth defect.

Some medical events may jeopardise the subject or may require an intervention to prevent one of the above characteristics/consequences. Such events (referred to as 'important medical events') should also be considered as 'serious' in accordance with the definition.

SAEs must be no	tified i	mmediat	ely	(and with	nin .	24	hrs) by	y telepl	none	or	email	to
the Sponsor's Resp	ponsible	Physic	ian,		(Γel:					E-ma	ail:
), Stu	dy Mo	nitor,			(`						
Email:)	and	l	Diamo	nd		Pharm	a	Servi	ces		by
	This	should	be	followed	by	a	written	report	withi	n 3	worki	ing
days.												

AEs which meet all of the following criteria

- Serious
- Unexpected (i.e. is not consistent with the investigator's brochure)
- There is at least a reasonable possibility that there is a causal relationship between the event and the medicinal product

will be classified as Suspected Unexpected Serious Adverse Reactions (SUSARs) and should be reported to the REC and to the MHRA in accordance with applicable regulatory requirements for expedited reporting. It is the Sponsor's responsibility to report SUSARs to the REC and MHRA, although this responsibility will be delegated to the Investigator.

To ensure no confusion or misunderstanding of the difference between the terms "serious" and "severe," which are not synonymous, the following note of clarification is provided:

The term "severe" is often used to describe the severity of a specific event (as in mild, moderate, or severe myocardial infarction); the event itself, however, may be of relatively minor medical significance (such as severe headache). This is not the same as "serious," which is based on patient/event outcome or action criteria usually associated with events that pose a threat to a patient's life or functioning. Seriousness (not severity) serves as a guide for defining regulatory reporting obligations.

Monitoring of Subjects with Adverse Events

In the event of any abnormalities considered to be clinically significant by the investigating physician, subjects will be followed up with appropriate medical management until:

- It has resolved/returned to normal or baseline.
- The event has stabilized at a level acceptable to the Investigator and is not considered to be clinically significant.

Pregnancy

Pregnancies must be reported immediately and should be followed up to determine outcome, including spontaneous or voluntary termination, details of the birth, and the presence or absence of any birth defects, congenital abnormalities, or maternal and/or newborn complications.

Confidential Page 55 of 73

Pregnancy outcomes must be collected for females who took the study drug and the female partners of any males who took the study drug. Consent to report information regarding these pregnancy outcomes should be obtained from the mother.

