9.2.3 Study Stopping Criteria

Part 1:

GB-HV-01 Clinical Study Protocol
RD 676/25641 Version: FINAL 6.0 / 05 April 2016 Page 32 of 73

• Dose Escalation will stop if 3 or more subjects in a cohort experience the same moderate adverse event that is deemed possibly, probably or definitely related to IMP treatment.

- Dose Escalation will stop if 1 or more subjects in a cohort experience severe adverse event that is deemed possibly, probably or definitely related to IMP treatment.
- Dose escalation would stop if 1 or more than 1 subject in the cohort experience a drug related SAE or a clinically significant drug-related non-SAE.
- Dose escalation will stop if the C_{max} and/or AUC values in each cohort reach or exceed those observed in the dog following 9.1 mg/kg/day 14 day repeat dosing, equating to a gender-averaged AUC(0-t) of 2450 ng*hr/mL and Cmax of 558 ng/mL on Day 14.

Part 2:

- The study will be stopped if 3 or more subjects experience the same moderate adverse event
- The study will be stopped if 2 or more subjects experience a severe adverse event.
- The study will be stopped if 1 subject experiences a drug related SAE or a clinically significant drug-related non-SAE.
- The study will be stopped if the Cmax and/or AUC values reach or exceed those observed in the dog following 9.1 mg/kg/day 14 day dosing, equating to gender-averaged AUC(0-t) of 2450 ng*hr/mL and Cmax of 558 ng/mL on Day 14.

During the clinical conduct of the study, all Investigators will be required to immediately inform the Chief Investigator, the sponsor and Simbec of any moderate, severe, SAE or clinically significant non-SAE. This notification is required in order to allow coordination of information and assessment on whether the stopping criteria has been met.

The procedure for the ongoing and interim data review in Part 2 will be fully documented to a dose review manual, approved by all parties.

The study will be discontinued if any unacceptable safety findings are identified. The Chief Investigator, Principal Investigators and the Sponsor will make this decision jointly. A written document signed by the Investigator (or deputy) and Sponsor will be produced ratifying the decision.

Please see Section 9.4.3 for possible reasons for discontinuation of an individual subject.

9.3 Discussion of Study Design, including the choice of Control Groups and Dose Leaders

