9.7.1.4.3 Vital signs

Vital signs assessments will include: Systolic and diastolic blood pressure, pulse, O_2 saturation, oral temperature and respiratory rate.

Measurements will be recorded in the supine position after 5 minutes (mins) rest. Blood pressure, pulse, O₂ saturation and temperature will be measured using an automated validated device, with an appropriately sized cuff.

9.7.1.4.4 12-lead ECG

12-lead ECG assessments will include: Heart rate, PR interval, QRS width, QT interval, and OTcB interval.

ECGs will be recorded in the supine position after 5 mins rest.

ECG recordings will be made using a MAC 5500 or equivalent. Each ECG trace should be labelled with the study number, subject initials and subject number. An investigator will

Confidential Page 56 of 73

provide an interpretation of each tracing. Clinically significant abnormalities should be recorded on the AE page.

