In addition, the number and percentage of subjects reporting TEAEs will be tabulated by maximum severity and strongest relationship to study drug. For the summary of TEAEs by severity, if a subject has multiple events occurring within the same SOC or preferred term, the event with the highest severity will be counted. Similarly, for TEAEs by relationship to study drug, if a subject has multiple events occurring within the same SOC or preferred term, the event with the highest association to study drug will be counted.

Biochemistry, haematology and urinalysis parameters will be listed with any out of normal range values flagged. Laboratory test results that are out of normal range will also be presented separately along with normal reference ranges. Descriptive statistics of absolute and change from baseline (pre-dose) values for each biochemistry and haematology parameter at each time point, up to and including day 15, will be tabulated by dose.

GB-HV-01 Clinical Study Protocol Confidential RD 676/25641 Version: FINAL 6.0 / 05 April 2016 Page 64 of 73

Frequencies of the total number of subjects randomised, completed, and prematurely discontinued (including reason for discontinuation) from the study will be summarised by dose. Additionally the frequency of subjects within each analysis population (safety, PK) will be summarised by dose.

Demographic data will be listed and descriptive statistics will be tabulated for the continuous variables age, height, weight and BMI and frequencies for the categorical variable race. These descriptive statistics will be presented by dose and overall.

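### AE severity is graded only by effect on daily routine, so an asymptomatic laboratory or ECG event is Mild whatever its size; this blunts the severity tables and, in Part 2, the moderate and severe counts for events not judged drug-related

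*Protocol*

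**What the plan says.** Section 9.7.1.4.1 asks the CRF to record "Severity of event, to be assessed by the investigating physician in accordance with the definitions below", and then closes the list: "The following are the only grades which should be used to describe AE severity". Each AE gets exactly one grade. Mild reads "The AE does not interfere with the subject's daily routines. It causes no more than slight discomfort". Moderate reads "The AE interferes with some aspects of the subject's daily routines". Severe requires that the daily routine cannot be carried out.

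The same section brings laboratory results into this scale: "All abnormal laboratory findings considered to be clinically significant must be recorded as AEs". Section 9.7.1.4.2.1 (laboratory) and Section 9.7.1.4.4 (12-lead ECG) say likewise: "Clinically significant abnormalities should be recorded on the AE page". No section gives a criterion for grading such an event by the size of the abnormality.

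The grade is used in two places:

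- Section 9.9.1.3: "the number and percentage of subjects reporting TEAEs will be tabulated by maximum severity". The overall AE summary also counts subjects by severity.
- Section 9.2.3, which counts moderate and severe events towards stopping in both parts. For Part 2: "The study will be stopped if 2 or more subjects experience a severe adverse event". The Part 2 moderate count is three or more subjects with the same event. Neither Part 2 count asks for relatedness to the study drug; both Part 1 counts do.

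**The concern.** Safety and tolerability are the primary objective, and Section 9.9.1.1 lists laboratory data, ECG data and AEs among the primary safety variables. A scale built on daily routine suits symptoms. It carries no information about an abnormality that the subject cannot feel. If every such event is Mild, a severity table showing only mild events says nothing about whether the laboratory or ECG AEs behind it were small or marked.

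The Part 2 counts matter for a second reason. Because they need no causality judgement, they act as a backstop when an event has been attributed to something other than the drug. That attribution is plausible here: the causality table rates as Unlikely an event easily explained by the subject's clinical state, and Part 2 enrols IPF patients aged 45 to 85. A class of event that cannot enter those counts loses the backstop.

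**Working it through.** The plan states no figure to reproduce (Section 9.9.2: no formal sample size calculation), so the check sets the definitions beside the rules that use them.

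**1. Which grade fits which event (9.7.1.4.1)**

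| Event | Interferes with routine | More than slight discomfort | Grade that fits |
|---|---|---|---|
| Laboratory or ECG abnormality, no symptoms, no functional effect | No | No | Mild only |
| Some aspects of routine affected | Yes | Either | Moderate |
| Routine cannot be carried out | Yes | Either | Severe |
| More than slight discomfort, routine unaffected | No | Yes | None |

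Row 1 holds whatever the size. Row 4 is a gap: Mild excludes the event through its discomfort limit, Moderate through its interference condition, yet one grade is compulsory.

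**2. What the tables then show.** Take two asymptomatic ECG events judged clinically significant, with QTcB of 485 ms and 520 ms (values chosen for illustration). Both are Mild, so the severity table treats them alike. The QTcB frequency table in 9.9.1.3 uses bands above 450, 480 and 500 ms: 485 exceeds the first two and 520 exceeds all three. The data that separate them are collected and reported; the AE grade does not use them.

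**3. Which stopping criteria such an event can meet (9.2.3)**

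| Criterion | Subjects | Relatedness needed | Depends on grade | Can be met |
|---|---|---|---|---|
| Part 1, same moderate AE | 3 in a cohort | Yes | Yes | No |
| Part 1, severe AE | 1 in a cohort | Yes | Yes | No |
| Part 1, drug-related SAE or clinically significant drug-related non-SAE | 1 in a cohort | Yes | No | Yes |
| Part 2, same moderate AE | 3 | No | Yes | No |
| Part 2, severe AE | 2 | No | Yes | No |
| Part 2, drug-related SAE or clinically significant drug-related non-SAE | 1 | Yes | No | Yes |
| Unacceptable safety findings | Not fixed | No | No | Yes, by joint decision |

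**4. What is lost.** These abnormalities become AEs only if clinically significant.

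- Part 1: the moderate and severe counts require relatedness. An event that could have counted at a higher grade is both clinically significant and drug-related, so a single subject already meets the grade-independent criterion. Nothing material is lost.
- Part 2, drug-related: the same holds. One subject is enough, and that threshold is passed whenever two or three subjects are affected.
- Part 2, not judged drug-related: the two counts are the only criteria with a fixed number of subjects and no relatedness condition. A non-serious asymptomatic event cannot reach either. This is the gap.

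In a rare case an asymptomatic event is serious only as an important medical event and is not judged drug-related. It also stays outside the counts, but SAE reporting brings it to the sponsor within 24 hours. The point does not rest on it.

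**The case against.** The strongest reply is that the scale does little harm, because the protocol has other routes:

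- One subject with a clinically significant drug-related event triggers stopping whatever the grade. That is more sensitive than the two- or three-subject counts.
- Important medical events count as serious irrespective of severity (9.7.1.4.1).
- Investigators must immediately notify any clinically significant non-SAE, with no condition on grade or causality (9.2.3).
- The Part 2 interim review sees laboratory, ECG and spirometry data directly (9.2.2).
- Section 9.9.1.3 provides flagged listings, change from baseline, a separate presentation of out-of-range laboratory results, and QTcB categories.

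All of this stands, and it rules out three stronger readings that a reader might infer. The first is that marked laboratory or ECG events escape the stopping rules generally; the table of criteria shows that they do not. The second is that their size goes unreported; it is reported, though not in the AE severity tables. The third is that Part 1 events were under-graded. Section 7 says that AEs up to 10 mg were mild, but it also reports no significant change from baseline in ECG, biochemistry or haematology, so nothing there points to a marked abnormality hidden by its grade.

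Two further objections have weight. A numeric scale is partly a design preference. And if size-based grades entered Part 2 counts that need no relatedness, abnormalities unrelated to the drug could stop the study. That is a reason to decide the question openly.

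The reply does not give the severity tables the missing information, close the gap between Mild and Moderate, or let the Part 2 counts register asymptomatic events not judged drug-related.

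**Conclusion.** The point holds as an inexpensive improvement to the primary safety output, not as a failure of the stopping rules. Its size is structural: for asymptomatic laboratory and ECG AEs three grades reduce to one, and one kind of symptomatic event has no grade. The stopping consequence is confined to Part 2 non-serious asymptomatic events not judged drug-related, for which the general clause on unacceptable safety findings still applies. How often such events would occur cannot be taken from the documents, so no probability is attached.

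This rests on three assumptions. Investigators apply the definitions as written, as the protocol requires. The abnormality has no functional consequence; one that disrupts daily routine can be graded higher. And drug-related in the one-subject criterion covers at least the relatedness categories named in the Part 1 counts, since 9.2.3 does not define it there.

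**What to change.** In Section 9.7.1.4.1:

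- Keep the functional scale for symptomatic AEs.
- Make the Mild and Moderate definitions contiguous, so that every event fits exactly one grade.
- State that laboratory and ECG AEs are graded by size of abnormality on one prespecified scale chosen by the sponsor. Apply it to Part 2 and, where Part 1 values are available, to Part 1 as well, so that the severity tables stay comparable across the study.

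Reconcile 9.7.1.4.1 with 9.2.3 by stating whether those grades enter the Part 2 moderate and severe counts. The thresholds and that decision belong to the sponsor and the Chief Investigator.

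The cost is an amended definitions table and matching CRF guidance, with no new measurement. Some AEs will be graded higher than now, so the severity tables may look less favourable, and Part 1 events already graded may need re-grading. If the grades are allowed into the Part 2 counts, the chance of stopping on unrelated abnormalities rises, and this should be weighed when the decision is made.

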9.7.1.4.2 Laboratory Safety Assessments

9.7.1.4.2.1 Routine Laboratory Safety Screen

Routine laboratory safety screen samples will be analysed by the local laboratory according to their local procedures. Printed laboratory Reports will include normal reference ranges.

A decision regarding whether the result outside the reference range is of clinical significance or not shall be made by the investigator and the report will be annotated accordingly. Clinically significant abnormalities should be recorded on the AE page. The reference ranges for local laboratory parameters will also be filed in the Investigator Site File.

Haematology: Haematology assessments will include: Haemoglobin (HGB), haematocrit (HCT), mean cell volume (MCV), mean cell haemoglobin (MCH), mean cell haemoglobin concentration (MCHC), red blood cells (RBC), white blood cells (WBC), neutrophils (NEUT), lymphocytes (LYMP), monocytes (MONO), eosinophils (EOS), basophils (BASO) and platelets (PLT).

Biochemistry: Biochemistry assessments will include: Total protein (TP), albumin (ALB), total bilirubin (BIL-T), alanine transaminase (ALT), aspartate transaminase (AST), gamma glutamyl transferase (GGT), glucose (GLU), sodium (NA), potassium (K), bicarbonate (HCO₃), urea and creatinine (CREA).

Urinalysis: Urinalysis assessments will include: protein, GLU, specific gravity, ketones, urobilinogen, bilirubin, pH and blood). In the event that the 'dipstick' was positive, RBCs, WBCs, epithelial cells, crystals, bacteria and casts will be examined microscopically. The microscopy will be performed by the local laboratory according to their local procedures.

Urinalysis will be performed by the local laboratory according to their local procedures.

